7. Clinic eligibility and consent visit

- Visit will be at Vanderbilt Clinical Research Center, Medical Center North 3rd Floor.
- The PPCCT research staff member will meet with the participant and describe the study protocol in lay terminology, including the purpose of the study, the study design and the biospecimen and data collection protocols in the study.
- The risks and benefits of the study are discussed prior to obtaining signatures on the consent form. The participant will be told that participation is voluntary
- Further evaluate the interest in participation.
- Review Inclusion / Exclusion Criteria.
- The research staff will provide ample time for the participant to have questions answered prior to enrollment.
- Obtain written informed consent.
- The research staff will also provide the study participant with a copy of the consent form.
- During the clinic visit, pregnancy test will be done on the female candidates. The participants with a positive pregnancy test will be informed of their ineligibility to participate this study.
- 5 ml of blood from the participant will be drawn in a green top tube and will be delivered to the Vanderbilt hospital laboratory to measure serum creatinine level for renal function assessment.

[figure not shown]
8. Renal Function Assessment

- The PPCCT research staff will abstract the lab result of serum creatinine level from the StarPanel approximately 2 hours after the blood sample is delivered to the hospital lab.
- The estimated Glomerular Filtration Rate (eGFR) for each participant will be calculated based on the serum creatinine level, the gender, age, and the race of the participant.
- The participants with an eGFR < 50 will be ineligible for this study.

9. Exclusion of participants with decreased renal function and positive pregnancy test (women only)

- On the next day following the clinic visit #1, the research staff will call the participant with eGFR < 50 and inform him/her of his/her ineligibility to participate this study due to the decreased renal function or positive pregnancy test if a participant is a woman (SCRIPT for POST CLINIC VISIT #1 INELIGIBILITY CALL, Appendix B).

B. Recruitment Procedures for patients with adenoma or/and hyperplastic polyp from the Vanderbilt University Hospital

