- After the physician has signed the prescription and the participant has provided written informed consent, the research staff fax the prescription and copy of signed consent form to Vanderbilt Investigational Drug Services (VIDS) during the first clinic visit (day 1, week 0).
- VIDS Call the research staff and send the Mg/placebo capsules to CRC on the day of appointment. The research staff gives the participant capsules at the Clinical Research Center of Vanderbilt University Medical Center and an Instruction for taking pill sheet (Appendix E) will be given to the participant and taken home.
- Pharmacist will send magnesium or placebo capsules to participants by Fedex if the participant leaves clinic visit prior to dispense.

2nd time to dispense the capsules (During the second clinic visit, week 6)

- Research staff notify Vanderbilt Investigational Drug Service (VIDS) to anticipate a prescription for the day of participant's second visit (week 6)
- Research staff provides the physician with the information necessary to complete a prescription.
- After the physician has signed the prescription, the research staff fax the prescription to Vanderbilt Investigational Drug Services during the second clinic visit (week 6).
- VIDS Call the research staff and send the Mg/placebo capsules to CRC on the day of appointment.
- The research staff gives the participant capsules at the Clinical Research Center of Vanderbilt University Medical Center and an Instruction for taking pill sheet (Appendix E) will be given to the participant and taken home.

- Pharmacist will send magnesium or placebo capsules to participants by Fedex if the participant leaves clinic visit prior to dispense.

If needed, an extra supply of Magnesium/Placebo supplements will be sent to the participants by Fedex to make participants have enough until their clinic visit.

sure
pills

[figure not shown]

Figure E2. The planned study design

Table E2. Magnesium treatment dosage based on baseline Ca/Mg ratio and calcium intake level and estimated Ca/Mg ratio after use of magnesium supplementation.

Baseline Ca/Mg ratio	Ca intake (mg/day)	Treatment dosage (pill size * number)	Resulting ratio	Ca intake (mg/day)	Treatment dosage (pill size and number)	Resulting ratio
2.6-2.8	700	size 1 (blue)*1	2.08	1400	size 00*1	2.25
2.6-2.8	800	size 1 (blue)*1	2.14	1500	size 00*1	2.27
2.6-2.8	900	size 1 (blue)*1	2.19	1600	size 00*1	2.3
2.6-2.8	1000	size 1 (blue)*1	2.23	1700	size 00*1	2.32

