- Contact the pharmacist at the VIDS and fax the Prescription once the signed Informed Consent Form is obtained. The VIDS will deliver pills (Magnesium glycinate or placebo) to the CRC. The participant will be given magnesium/placebo pills and verbal instructions. An Instruction Sheet for Taking Pill will also be given and taken home (Appendix E).
- Obtain the signed Payment Authorization Form (Appendix J).
- Measure the body size and vital signs for each participant and record in the Biological Specimen Collection Form H_1 (Appendix H).
- Obtain the urine, stool, and saliva samples and temporarily store the samples in the freezer at CRC. The completed Clinic Visit Questionnaire Form (Appendix F) will be reviewed by the research staff. Particularly, record medications and supplements currently used by the participant and the dosage.
- The urine, stool, saliva sample collection information will be recorded in the Biological Specimen Collection Form H_1 by research staff.
- Cognitive assessment will be performed and the collected information will be recorded in a Montreal Cognitive Assessment Form for Clinic Visit #1 (Appendix F) by a PPCCT research staff.
- Health assessment will be performed and the collected information will be recorded in a Health Assessment Form for Clinic Visit #1 (Appendix F) by a PPCCT research staff. The procedure was only conducted during 6/18/2012 to 9/30/2012 because of the staff's departure. ”
- The blood draw, skin swab sample collection, and hair and nail sample collection procedures will be performed. Sample collection protocols for blood, hair, and nail will be applied and samples will be obtained respectively. The collection information will be recorded in the Biological Specimen Collection Form H_1. (Details in the Biological Specimen collection protocols).

- The rectal biopsy procedure will be performed by a well trained gastroenterologist. The rectal biopsies and rectal swabs will be obtained. The collection information will be recorded in the Biological Specimen Collection Form H_1. The participant will be closely observed for 30 minutes at the Clinical Research Center after the procedure. A Post Procedure Safety Handout will be given to the participant and taken home (Appendix F).
- Give participant a packet for next biological sample collection at week 6.
- Fill out and review the Biological Specimen Collection Form H_1.
- Complete the Clinic Progress Note (Appendix F)

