4. Biological specimens handling and processing (See details in the Biological Specimen Collection Protocols)

- *Rectal Biopsies and swabs*: Deliver the collected rectal biopsies and rectal swabs to the Molecular Epidemiology Lab. The Rectal biopsies handling and processing protocol will be applied.
- *Blood samples*: Deliver the collected blood samples to the Molecular Epidemiology Lab. The blood sample handling and processing protocol will be applied.
- *Urine samples*: Deliver the urine samples to the Molecular Lab. The Urine sample handling and processing protocol will be applied.
- *Stool samples*: Deliver the stool samples to the Molecular Epidemiology Lab. The stool sample handling and processing protocol will be applied.
- *Saliva samples*: Deliver the saliva samples to the Molecular Epidemiology Lab. The saliva sample handling and processing protocol will be applied.
- *Hair samples*: Deliver the hair samples to the Molecular Epidemiology Lab. The hair sample handling and processing protocol will be applied.
- *Nail samples*: Deliver the nail samples to the Molecular Epidemiology Lab. The hair sample handling and processing protocol will be applied.
- *Skin Swabs*: Deliver the skin swab samples to the Molecular Epidemiology Lab. The skin swab sample handling and processing protocol will be applied.
- *Serum creatinine test*: Deliver 1.5 -2 ml of plasma from the green top tube to the Vanderbilt Hospital Lab for renal function panel and serum magnesium assays.
- *Pregnancy test*: Deliver 1 ml of plasma from the green top tube to the CRC laboratory for pregnancy test if the participant is a woman.
- Complete the Biological Specimen Transit Log Form and Laboratory Log.

5. Eligibility Further confirmed by the renal creatinine clearance

- The PPCCT research staff receive the results of pregnancy test for the female participants from CRC laboratory.
- The PPCCT research staff get access to the StarPanel on the next day following the clinic visit #1, record the serum creatinine result, and enter it into the Redcap database. The estimated glomerular filtration rate (eGFR) will be calculated based on the serum creatinine level, age, gender, and race.
- If either the creatinine clearance is < 50 or the pregnancy test is positive, a phone call will be placed to inform the participant of his/her ineligibility due to the decreased renal function or pregnancy. [Script for Post Clinic Visit #1 Ineligibility Call (Appendix B)]

--- Clinic Visit #2 (Week 6)

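### Visit 1 capsules are released on signed consent, while the measured eGFR < 50 exclusion is acted on only by a next-day call

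*Combined protocol and SAP*

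**What the plan says.** **Release of capsules.** Two places set the trigger, and both rest on consent.

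- Section 6.0 E, Intervention Protocol, item 4 (first dispensing, week 0): "After the physician has signed the prescription and the participant has provided written informed consent, the research staff fax the prescription". The pharmacy then delivers on the appointment day. For early leavers: "Pharmacist will send magnesium or placebo capsules to participants by Fedex if the participant leaves clinic visit prior to dispense".
- Section 6.0 F, Clinic Visit #1, first bullet of step 3: "Contact the pharmacist at the VIDS and fax the Prescription once the signed Informed Consent Form is obtained". The same bullet continues: "The participant will be given magnesium/placebo pills and verbal instructions". The blood draw is listed several bullets later.

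**Reading the renal result.** The sample goes to the hospital laboratory from visit 1 (Clinic Visit #1, step 4, which sends 1.5 to 2 ml "of plasma from the green top tube to the Vanderbilt Hospital Lab for renal function panel and serum magnesium assays"). Two sections differ on when the result is read.

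- Section 6.0 B, recruitment procedure A, step 8: staff "abstract the lab result of serum creatinine level from the StarPanel approximately 2 hours after the blood sample is delivered to the hospital lab".
- Section 6.0 F, Clinic Visit #1, step 5: staff "get access to the StarPanel on the next day following the clinic visit #1".

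**Acting on it.** Both sections act by telephone. Procedure A, step 9 is explicit on timing: "On the next day following the clinic visit #1, the research staff will call the participant with eGFR < 50".

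**The criterion.** Section 4.0 excludes creatinine clearance below 50, and procedure A, step 8 applies the same cut-off to eGFR. Section 7.0 relies on excluding renal insufficiency as a safeguard against magnesium toxicity.

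**The concern.** The measured eGFR exists to catch renal impairment that the earlier screens miss. Known chronic renal disease is already removed at record review, at the telephone interview and, for hospital patients, by the database filter. The laboratory value is first obtained at visit 1, and as written it takes effect after the supplement has been handed over.

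A person excluded on a renal safety criterion can therefore leave with capsules and take some of them. That person has also been allocated already, because the prescription faxed at the visit carries the treatment assignment (Section 6.0 E, item 2). What is at stake is a breach of a named eligibility criterion and a short avoidable exposure, plus a few allocations to people who should not have been enrolled.

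The point concerns eGFR only. Procedure A, step 7 does the pregnancy test during the visit.

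**Working it through.** **1. Order of events, from the documents' own timing**

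| When | Event | Source |
|---|---|---|
| Day 0 | Consent signed, prescription faxed, capsules given | 6.0 E item 4; 6.0 F visit 1 step 3 |
| Day 0 | Blood drawn, plasma sent to hospital laboratory | 6.0 F visit 1 steps 3 and 4 |
| Day 0, about 2 hours after laboratory delivery | Creatinine read | 6.0 B procedure A step 8 |
| Day 1 | Creatinine read (conflicting text) | 6.0 F visit 1 step 5 |
| Day 1 | Ineligibility call | 6.0 B procedure A step 9 |

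The stated conditions for release are a physician's signature and written consent. Neither is tied to the creatinine result. On either reading of when the result is seen, the only action is a telephone call, and procedure A places it on day 1. The courier route has no hold either.

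**2. Possible exposure before the call**

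Inputs:
- Dose Reduction Guidelines table (Section 6.0 E): lowest daily dose, one blue capsule, 77.25 mg. Highest, one blue plus three orange: 77.25 + 3 × 104.10 = 389.55 mg, which matches the table.
- Section 6.0 F, visit 1 step 2: capsules are taken daily with breakfast.

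| Doses before the call | Lowest dose | Highest dose |
|---|---|---|
| 0 | 0 mg | 0 mg |
| 1 | 77.25 mg | 389.55 mg |
| 2 | 2 × 77.25 = 154.50 mg | 2 × 389.55 = 779.10 mg |

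Two doses assume one on the visit day, one at the next breakfast, and a call that comes after that breakfast and reaches the participant the same day. A visit-day dose is plausible because participants are reminded to arrive having fasted for about 8 hours. Someone not reached on day 1 could take more. In the placebo arm the exposure is 0 mg magnesium.

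**3. Effect on the sample size**

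Planned enrolment is 288 (152 GG, 136 GA/AA), against 120 needed in each genotype group:

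- Total: 288 − 240 = 48
- GG: 152 − 120 = 32
- GA/AA: 136 − 120 = 16

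Recruitment procedure A, step 4 also repeats mailing waves until 120 per genotype group complete. The documents give no rate of unrecognised eGFR < 50, so no head count can be derived.

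**4. Effect on bias**

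The exclusion depends on a baseline laboratory value and is applied by staff blinded to assignment (Section 6.0 E). Removing these participants should therefore not differ between arms in any material way.

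**The case against.** The strongest reply is that little is left to fix. Known renal disease is screened out repeatedly, the criteria are reviewed again at the visit before consent, and a physician signs the prescription. Every participant is also telephoned the day after the baseline visit (Section 6.0 G). Section 7.0 places the toxicity concern in severe renal insufficiency, and the documents do not say that an eGFR just under 50 is severe. The upper figure of 779.1 mg combines the largest dose in the table with the most unfavourable timing. All of this stands, and it is why the harm is rated small.

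A second reply is that the order is inferred. Procedure A reads the result within about 2 hours, no clock time is given for the handover, and the bullets in step 3 are not a strict timetable. The pharmacy's operating procedures, the pill instruction sheet and the call script are not in the document, and any of them could contain a hold, a delayed first dose or a return of capsules. This limits certainty. It does not remove the gap, because both dispensing sections name consent as the trigger, and even the section with the 2-hour lookup waits until the next day to act.

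A third reply is that one sentence telling participants not to start until eligibility is confirmed would be enough. That would remove most of the exposure, but it relies on the participant and still leaves an excluded person holding supplement.

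**Conclusion.** The concern holds. As written, the plan lets a participant with unrecognised eGFR < 50 be allocated and leave with capsules before the exclusion is applied. The likely exposure is 0 to 2 daily doses: 0 to 154.5 mg elemental magnesium at the lowest active dose, 0 to 779.1 mg at the highest, and none on placebo. The number affected is unknown. The effect on power is negligible and little or no bias between arms is expected.

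The conclusion rests on the triggers stated in the visible text, with no hold in the unseen pharmacy procedures, instruction sheet or call script. The two-dose bound also assumes that the call succeeds on day 1. The change is worth making because it is cheap and closes a gap in a named safety exclusion, not because the expected harm is large.

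**What to change.** Amend Section 6.0 E item 4, Section 6.0 F Clinic Visit #1 steps 3 and 5, and Section 6.0 B procedure A steps 8 and 9 as follows.

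- Release capsules only after a passing eGFR and, for women, a negative pregnancy test have been recorded.
- Use the same-day creatinine lookup in procedure A, step 8 throughout, and remove the conflicting next-day wording in visit 1, step 5.
- If the participant has left, send the capsules by the existing courier route, but only after a pass.
- Keep the ineligibility call as notification, with no capsules yet released.

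Optionally, issue the allocation only after eligibility is confirmed. Because the assignment is on the prescription, this also changes the prescription and pharmacy workflow. Otherwise, log anyone allocated before a failing result (date, reason, doses taken) and show them in the participant flow.

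**Cost.** No new test or sample is needed. The wait at visit 1 is at least about 2 hours, counted from delivery to the laboratory, so drawing, separating and transporting the sample add to it. Drawing blood early would let part of the wait overlap with the cognitive assessment, sampling, biopsy and 30-minute observation. The courier alternative delays the first dose slightly. Because visit 3 is booked before visit 1 takes place, it shortens the intervention by the same amount unless that visit is moved.

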 - Biopsies will be embedded in one paraffin block. Pay attention to embedding orientation of the tissues so that well-oriented longitudinal crypts can be sectioned.

- The cassettes are labeled with a # 3 pencil on the front side of each block with the participants ID # and visit date.
- Initial water residues are removed from tissues by flushing graded alcohols (70, 80, 95, and 100%) sequentially into the reaction chamber.
- Each alcohol remains in the tissue-containing chamber for approximately 45 minutes, and a 5-minute draining period is allowed between alcohol changes. Two xylene exchanges are followed by two 60C heated paraffin exchanges, each one hour in duration.
- The paraffin-infiltrated tissues are removed from the Hypercenter, embedded into paraffin blocks, and prepared for shipment.
- Blocks are then stored in the refrigerator in the core lab at 4 degrees C until ready for analysis.

Storage

- Blocks are stored in the core lab at 4 degrees C

Slide preparation

Biopsies will be sectioned with a microtome so that crypts will be longitudinally sectioned from base to lumen.

- Sections are then placed sequentially on positive charged slides and numbered from 1 to 26.
- Section levels are Five microns thick, and are taken approximately 50 microns apart. (Taking sections 50 microns apart to avoid double counting of crypts in biopsy specimens)
- The sections numbered 1, 11 and 21 will be used for H&E staining.
- Three slides per biomarker are prepared for processing each of the antibodies for Ki-67, Bax, COX2, TRPM7, pMLKL and the TUNEL assay.
- Multiple biopsies are collected and multiple sections will be prepared. In case of staining run failures, one backup serial section per slide for staining is prepared.
- All blocks and slides will be stored in a vacuum chamber at 4 degree C in a cold room until analysis.

Immunohistochemistry

Slides are then subjected to immunohistochemical analysis for the antibody of interest in the Molecular Epidemiology Lab at Vanderbilt. Ki-67 (mib1), bax, COX2, TRPM7, pMLKL expression is detected in colon crypt cells by using immunohistochemical (IHC) technique that stains positive cells a brown color. This permits visual identification of cells expressing these genes.

Expression of Ki-67, Bax and COX-2 in colon epithelial cells will be detected following the standard IHC protocol of EnVision™+ System, HRP (DAKO). After deparaffinization of the tissue slides, antigen retrieval is performed by heating the slides with a pressure cooker in the optimized buffer solutions: Retrievagen A pH6.5 (BD Pharmingen) for Ki-67, R-buffer A (PickCell Lab.) for COX-2, and Epitope Retrieval Solution (IHCWorld.com) for Bax. The primary antibodies of mouse monoclonal anti-Ki-67(BD Biosciences Pharmingen), mouse monoclonal anti-COX-2 (Zymed), and rabbit polyclonal anti-Bax (Santa Cruz) are applied with proper work dilutions. The TUNEL (TdT-mediated dUTP Nick-End Labeling) assay is conducted to measure apoptosis of colon epithelium using DeadEnd Colorimetric TUNEL System (Promega). The expression and co-existence of TRPM7 is detected using a sequential double immunofluorescent staining proposed by Vector Laboratories (Protocol: Double Immunofluorescent Labeling Using Primary Antibodies from Different Species: <http://www.vectorlabs.com/infopage.asp?dpID=53&locID=684325>). In brief, antigen retrieval is performed by heating the slides with a pressure cooker in 0.01 M citrate buffer (pH 6.0). The

slides are blocked with Avidin/Biotin Blocking Kit (Vector) and 5% normal goat serum, incubated with 1st primary antibody (rabbit polyclonal anti-TRPM6, Abcam), biotinylated goat anti-rabbit IgG (Vector), and fluorescein avidin DCS (Vector). For staining of second antigen, the blocking step is repeated with Avidin/Biotin Blocking Kit (Vector) and 5% normal rabbit serum, the slides are incubated with the 2nd primary antibody (Sheep polyclonal anti-TRPM7 (Abcam), biotinylated rabbit anti-sheep IgG (Vector), and Texas red avidin DCS (Vector). The slides are washed and coverslipped with the anti-fade and anti-photobleaching VECTASHIELD HardSet Mounting Medium with DAPI (Vector). A lab-constructed tissue microarray block composed of lymph node, kidney, lung, small intestine and known positive and negative colon adenoma tissues for these biomarkers is used as control slide. The control slide is stained in parallel with each batch using an Autostainer Universal Staining System (DAKO).

Scoring Procedures:

We will test the carcinogenesis-related biomarkers and use the vitro system to identify the most effective and optimized agents. (1) cell biological features: epithelial and stromal morphology; (2) immunophenotypes: CK5/14; CK8/18; Pan-CK; Vimentin; Smooth muscle actin detected by IF staining; (3) molecular signaling pathways; (4) organ-specific gene expression (5) carcinogenesis-related biomarkers; (6) stemness.

Measurement of Microbiomial Markers

Micorbiomial markers in rectal biopsy/swab samples will be measured at baseline, 3-month after the magnesium supplementation.

Measurement of other IHC biomarkers

IHC markers (e.g. CES1, CES2, DEC1, pMLKL) in rectal biopsy samples will be measured at baseline, 3-month after the magnesium supplementation.

Title of Study: Personalized Prevention of Colorectal Cancer Trial

IRB#:

Study Note

Date: Time:

Anoscopy with Rectal Biopsy for Study Protocol

Patient's Name:

Operator: [name]

Procedure: Anoscope was gently inserted into the anus. The obturator was then removed. Using a flexible biopsy forceps - model DBF-2.4-160-S (Cook Medical Inc.) , 8 specimens were obtained. Blood loss was minimal. The anoscope was removed. No complications noted. Patient was monitored per study protocol.

[name]

Title of Study: Personalized Prevention of Colorectal Cancer Trial

IRB#:

Study Note

Date: _____ Time: _____

Anoscopy with Rectal Biopsy for Study Protocol

Patient's Name:

Operator: [name]

Procedure: Anoscope was gently inserted into the anus. The obturator was then removed. Using a flexible biopsy forceps - model DBF-2.4-160-S (Cook Medical Inc.), 8 specimens were obtained. Blood loss was minimal. The anoscope was removed. No complications noted. Patient was monitored per study protocol.

[name]

--- Blood Sample Collection

Blood Draw Protocol

In the study, erythrocyte magnesium (a candidate biomarker for marginal magnesium deficiency) will be used as the primary endpoint to monitor magnesium status and the compliance of treatment, complimented by the secondary endpoint, serum magnesium. Blood samples will be collected at weeks 0, 6 and 12 during the course of magnesium treatment.

In the study, serum magnesium, vitamin D and plasma C-reactive protein will be measured as secondary endpoints to evaluate the effects of the reduction of dietary Ca/Mg intake ratio by magnesium supplementation.

A fasting blood (15 ml for each person) will be drawn into serum, EDTA, and heparin tubes. A blood sample will be collected on the biopsy collection day at the beginning and the end of the intervention phase respectively, at week 0 and week 12. An additional blood sample will be collected at the midpoint of the intervention phase, at week 6.

Location

Clinical Research Center (CRC) Medical Center North, 3rd floor on the Vanderbilt Campus

Scheduling

Participants will receive a schedule of planned blood draw, possibly fasting blood draw. Approved research staff with demonstrated competency will draw blood in CRC procedure rooms. A blood sample will be collected on the biopsy collection day at the beginning and the end of the intervention phase respectively, at week 0 and week 12. An additional blood sample will be collected at the midpoint of the intervention phase, at week 6. All visits on a given participant will be taken at the same time of day to avoid potential variability due to circadian rhythm.

Some participants, if willing, will provide two fasting blood samples in place of 1st and 3rd clinic visit collection. The first fast blood collection for the participant will take place less than or equal to 7 days prior to the baseline clinic visit. The last fasting blood collection will take place less than or equal to 7 days prior to the final clinic visit. Participants will receive \$25 for each blood draw.

Preparation

- Tourniquet
- Non-latex disposable gloves
- Syringe or Evacuated Tubes
- Needle holder
- 70% alcohol pads
- 20 or 21 Gauge needle for the forearm or 25 Gauge needle for the wrist or hand
- Red, Lavender and Green top collection tubes
- Labels
- 2 x 2 Gauze pads
- Adhesive Tape or Bandages
- Biohazard sharps collection container

Procedure

- Wash your hands thoroughly and don non-latex disposable gloves to prevent cross-contamination.
- Ask the ambulatory patient to sit in a chair and support his arm securely on an armrest or tabletop.

- Assess the patient's veins to determine the best puncture site. Observe the skin for the vein's blue color, or palpate the vein for a firm rebound sensation.
- Tie a tourniquet 2" proximal to the area chosen. If the tourniquet fails to dilate the vein, have the patient open and close his fist repeatedly. Then ask him to close his fist as you insert the needle and to open it again when the needle is in place.
- Clean the venipuncture site with an alcohol pad using friction for 30 seconds. Wipe in a circular motion, spiraling outward from the site. Allow to dry before performing venipuncture.
- Immobilize the vein by pressing just below the venipuncture site with your thumb and drawing the skin taut.
- Position the needle holder or syringe with the needle bevel up and the shaft parallel to the path of the vein and at a 30-degree angle to the arm. Insert the needle into the vein. If you are using a syringe, venous blood will appear in the hub; withdraw the blood slowly, pulling the plunger of the syringe gently to create steady suction until you obtain the required sample. Pulling the plunger to forcibly may collapse the vein. If you're using a needle holder and an evacuated tube, grasp the holder securely to stabilize the vein, and push down on the collection tube until the needle punctures the rubber stopper. Blood will flow into the collection tube automatically.
- Remove the tourniquet as soon as the blood flows adequately to prevent stasis and hem concentration, which can impair test results. If blood flow is sluggish, leave the tourniquet in place longer, but always remove it before withdrawing the needle.
- Continue to fill the required tubes, removing one and inserting another. Gently rotate each tube as you remove it to help mix the additive.
- After you've drawn the sample, place a gauze pad over the puncture site, and slowly and gently remove the needle from the vein. When using an evacuated tube, remove it from the needle holder to release the vacuum before withdrawing the needle from the vein.
- Apply gentle pressure to the puncture site for 2 to 3 minutes or until bleeding stops. This prevents extravasation into the surrounding tissue, which causes hematoma.
- After the bleeding stops, apply an adhesive bandage.
- If you have used a syringe, transfer the sample to a collection tube. Detach the needle from the syringe, open the collection tube, and gently empty the sample into the tube, being careful to avoid foaming, which may cause hemolysis.
- Label the patient chart with appropriate blood tube labels and record the time of collection on BIOLOGICAL SAMPLE COLLECTION FORM (Appendix H).
- Place the red and purple top tubes into black wet ice bucket and leave the green top tube at room temperature.
- Finally, check the venipuncture site to make sure a hematoma has not developed. If it has, then apply warm soaks.
- Discard syringes, needles, and used gloves in the appropriate containers.

Special Considerations

- If the patient has large, distended, highly visible veins, perform venipuncture without a tourniquet to minimize the risk of hematoma
- If the patient has a clotting disorder or is receiving anticoagulant therapy, maintain firm pressure on the venipuncture site for no less than 5 minutes after withdrawing the needle to prevent formation of a hematoma.

Blood processing

- Blood specimens will be stored in CRC refrigerator.
- All specimen's will be labeled with date, participant ID #

- Specimens will be processed within 4-6 hours after collection
- Serum will be collected after coagulation.
- Whole blood (EDTA tube) will be processed within 4-6 hours and separated into plasma, buffy coats (white cells).
- Erythrocytes will be retained (heparin tube). After separation, erythrocytes will be washed twice with cold solution (about 10 ml of 0.9% NaCl at 4°C). The erythrocytes will be then transferred to two 2-ml tubes and stored for future analyses. Both pipette tips and tubes are plastic, ordered from SARSTEDT (Germany). The magnitude of metal contamination of the SARSTEDT tubes has been examined in a previous study by using flame atomic absorption spectroscopy
- 1-2 ml aliquots of the serum/plasma sample will be pipetted into each of 9-labeled cryovials.
- Vials will be placed in specimen box for storage
- Study staff will then transport specimens to [name] [name], [name]
- Date, time and location of sample in the freezer will be recorded on the specimen log
- Samples will be stored at -80° C.
- Blood specimens will be stored until use in relevant assays.

Blood sample allocation

- One aliquot of erythrocytes will be assayed for total magnesium in NMS Labs, Inc.
- One aliquot of serum will be assayed for serum magnesium at the Vanderbilt Pathology Laboratory Services.
- One aliquot of plasma will be assayed for plasma vitamin D metabolite, 25(OH)D in [name] laboratory at Medical University of South Carolina.
- One aliquot of plasma will be assayed for plasma C-reactive protein at the Vanderbilt Pathology Laboratory Services.
- The remaining samples will be stored for additional assays in the Molecular Epidemiology core Laboratory freezer.

Laboratory Assay

Determination of Total Magnesium in Erythrocytes

Flame atomic absorption spectroscopy is the most widely used technique for measuring total magnesium. The sensitivity of magnesium measured by flame atomic absorption is sufficiently high so a graphite furnace is not required for determination. We will use erythrocytes which are washed twice using ice-cold solution before storage at -80°C. These assays are routinely conducted in NMS Labs, Inc. In brief, erythrocyte samples will be diluted with 0.5% Lanthanum Chloride Solution and analyzed by flame atomic absorption using a hollow cathode lamp source that emits light at a wavelength of 285.2 nm. The sample concentrations are determined by comparison of the absorbance of the sample with the calibration curve constructed from a series of standards. Magnesium calibrators are run at 0, 0.40, 1.0, 2.5 and 5.0 mg/dL. This assay is regularly validated through inclusion of external standards by using three levels of control: commercial serum at 1.8 and 4.7 mg/dL and in-house blood control at 4.0 mg/dL. The method has a coefficient of variation (CV) between runs of 3.0% at target concentrations of 1.8 and 4.7 mg/dL serum. The between run CV for the blood control is 2.4%. The means of the three controls are all within +/- 3.2%.

Serum magnesium

Serum magnesium will be determined by standard analytic method on the Beckman DXC 800 chemistry analyzer and 24-hour urine magnesium will be assayed by an atomic absorption spectrophotometer, both provided by the Vanderbilt Pathology Laboratory Services.

Measuring Plasma Vitamin D metabolite, 25-Hydroxyvitamin D (25(OH)D)

The radioimmunoassay (RIA) for plasma vitamin D metabolite, 25(OH)D, has been developed and validated in [name] laboratory. The RIA assay results compare well with those from a liquid-chromatographic procedure involving specific ultraviolet detection of 25(OH) D in plasma. This assay has been successfully applied in a number of epidemiological and clinical studies with excellent reproducibility, including all four previous studies on the association between blood 25(OH)D and risk of colorectal cancer or adenoma. Antibodies will be generated in a goat immunized with the vitamin D analog 23, 24, 25, 26, 27-pentanor-C(22)-carboxylic acid of vitamin D, coupled directly with bovine serum albumin. The ¹²⁵I-labeled tracer will be prepared by reacting a 3-amino-propyl derivative of vitamin D-C(22)-amide with Bolton-Hunter reagent. Calibrators will be prepared in vitamin D-stripped human serum. 25(OH) D will be quantitatively extracted from serum or plasma (50 μ l) with acetonitrile. The assay will consist of a 90-min incubation at room temperature with primary antiserum, followed by a 20-min incubation with a second antiserum and separation of bound from free fractions by centrifugation. The detection limit of the assay will be 2.8 mg/L for 25(OH) D.

Measurement of blood Vitamin D metabolite

Assays of blood vitamin D metabolite including 24,25-dihydroxyvitamin D (24,25(OH)D), 25-Hydroxyvitamin D (25(OH)D), and 1,25-Dihydroxyvitamin (1,25(OH)D) and vitamin D binding protein will be performed.

Measurement of Plasma CRP

Assays of CRP will be performed using immuno turbidimetric immunoassay based commercial assay kits purchased from Pointe Scientific, Inc, Canton, MI, applying autoanalyzers available in the Vanderbilt Pathology Laboratory Services.

Measurement of Red Blood Cell Heavy Metal

Assays of heavy metal will be performed using [Inductively Coupled Plasma Mass Spectrometry \(ICP-MS\)](#) at the Vanderbilt Mass Spectrometry Core laboratory.

Measurement of Serum Lipid Profile Markers

Assays of serum lipid profile markers (including uric acid, low-density lipoprotein cholesterol (LDL-C), high-density lipoprotein cholesterol (HDL-C), total cholesterol, triglycerides) will be performed in the [name] lipid lab at the Vanderbilt University.

Measurement of One-carbon Metabolites

Assays of blood one-carbon metabolites will be performed.

Measurement of Methylomic biomarkers

Assay of methylomic biomarkers in biospecimen will be performed.

Measurement of miRNA profiling

Assay of miRNA in biospecimen will be performed.

Measurement of circulating inflammatory biomarkers

Assay of circulating inflammatory biomarkers (e.g. GGT, HBVs, HCV, TNF and others) in biospecimen will be performed.

--- Urine Sample Collection

Urine Collection and Handling Protocol

The fasting urine samples will be collected prior to the treatment (week 0), the midpoint (week 6) and the end of intervention (week 12). Each urine sample will be collected in a sterile urine specimen container containing 100 mg ascorbic acid as a preservative.

Location

Clinical Research Center (CRC) Medical Center North, 3rd floor on the Vanderbilt Campus

Scheduling

Participants will receive a schedule of planned fasting urine collections. A urine sample will be collected on the biopsy collection day at the beginning and the end of the intervention phase respectively, at week 0 and week 12. An additional urine sample will be collected at the midpoint of the intervention phase, at week 6. All samples on a given participant will be taken at the same time of day to avoid potential variability due to circadian rhythm.

Preparation

Sterile specimen container 20 ml with 100 mg ascorbic acid

10-1.8ml cryovials vials

Specimen box

Labels

Permanent markers

Biohazard Bags

Procedure

Before the clinic visit, participants will be mailed:

- Sterile urine containers containing a preservative
- Zip-lock bags/ biohazard bags
- Insulated bag with ice packs
- Patients will be given written and verbal instructions for collection of urine samples
- Patients will be instructed to:
 1. Collect the fasting urine of the day.
 2. Place specimen in zip-lock bag / biohazard bag.
 3. Fill the urine collection questionnaire (Appendix G)
 4. Store specimen in the freezer until ready to leave for clinic.
 5. Place zip-locked bag in insulated bag with ice pack.
 6. Transport the sample to the clinic.
 7. Give specimen to study staff and receive clean container for next collection.

Urine Processing

- Urine specimens will be stored in CRC freezer.
- Specimens will be processed within 4-6 hours after collection.
- All specimen's will be labeled with date, participant ID #.
- 1-2 ml aliquots of the urine sample will be pipetted into each of 9-labeled cryovials.
- Vials will be placed in specimen box for storage.
- Remaining specimen will be discarded.
- Study staff will then transport specimens to [name] [name], [name].
